8. PHARMACOKINETIC ANALYSIS

This following section is organized based on the exploratory endpoints 6 and 7 in [Section 2.2](#).

8.1 Measurements and Collection Schedule

8.1.1 Blood Sample Collection

PK blood samples for the determination of plasma verposide and picroside II concentrations will be collected in 4 mL pre-chilled evacuated tubes containing K₂EDTA on Days 1 and 54 (\pm 1) or Day 56 of the Treatment Period prior to dosing (predose) and at 0.167, 0.25, 0.5, 0.75, 1, 1.5, 2, 2.5, 3, 3.5, 4, 5, 6, 8, 10, and 12 hours postdose. In addition, predose samples will be collected on Days 15 (\pm 2), 29 (\pm 2) and, 43 (\pm 2) of the Treatment Period.

The sampling schedule and/or collection intervals may be modified based on the results as the study progresses.

Samples must be protected from UV light during collection, processing, and storage.

8.1.1.1 Handling of Time Deviation

For verposide and picroside II PK blood samples, the actual sampling times will be assessed as available.

All concentration data will be included in the calculation of the PK parameters and the individual concentration-time plots (based on actual sample times), as well as in the mean concentration-time plots (based on nominal sample times); however, if there are any significant deviations (i.e., the actual sample time is closer to the next nominal time point than the intended nominal time point), concentration data may be excluded from mean concentration-time plots (based on nominal sample times). However if there are any significant time deviations that are judged to compromise the integrity of the PK results, the PK data for those patients will be handled as described in [Section 8.5.1](#).

8.1.2 Bronchoalveolar Sample Collection

Epithelial brushings samples for the determination verproside and picroside II concentrations will be collected at baseline at Check-in and on Day 55 or 56

The brushings (cellular material) will be collected from each of 4 quadrants of visible subsegments of the right middle or lower lobe. The brushings cell pellet will be stored at -70°C until processed or stored as indicated in the laboratory manual to be provided as a separate document.

Samples must be protected from UV light during collection, processing, and storage.

8.2 Bioanalytical Method

Plasma concentrations of verproside and picroside II will be determined using the bioanalytical method SOP (EDT) methods validated with respect to accuracy, precision, linearity, sensitivity, and specificity at Celerion, Lincoln, Nebraska, USA.

The validated analytical range (lower limit of quantitation [LLOQ] – upper limit of quantitation [ULOQ]) for verproside and picroside II is 50.0 – 20 000 pg/mL.

8.3 Investigational Product and PK Analyte Information

YPL-001 is a botanical drug substance containing a mixture of iridoids from the aerial parts of the plant Speedwell (*Pseudolysimachion rotundum var. subintegrum*). The principal pharmaceutically-active ingredient in YPL-001 is verproside, an iridoid. YPL-001 contains additional iridoids in lesser relative amounts.

[figure not shown]
Molecular formulae and the molecular masses of the six constituents of YPL-001 are provided in Table 1.

Table 1 Principle Active Constituents in YPL-001

Generic Name	Molecular Formula	Molecular Weight (g/mol)
Verproside	C ₂₂ H ₂₆ O ₁₃	498.43
Picroside II	C ₂₃ H ₂₈ O ₁₃	512.46
Catalpolside	C ₂₂ H ₂₆ O ₁₂	482.43
Isovanilloyl catalpol	C ₂₃ H ₂₈ O ₁₃	512.46
6-O-veratroylcatalpol	C ₂₄ H ₂₈ O ₁₃	526.17
Veratric acid	C ₉ H ₁₀ O ₄	182.17

The structure of verproside and related congeners are provided in Figure 1.

Figure 1 Structure of Verproside and Related Active Compounds in YPL-001

Note that only plasma and BAL verposide and picroside II concentrations are planned for analysis in this current study. However, other components of YPL-001 and its metabolites may also be analyzed, if required. If metabolite data are available, metabolite to parent ratios may be calculated for AUC_{0-t} , AUC_{τ} , and $C_{max\ ss}$.

Any dose dependent PK parameters such as clearance and volume of distribution will need adjustment for the content of verproside in the YPL-001 dose. Verproside content is 28.96 and 57.92 mg for the 80 and 160 mg YPL-001 dose levels, respectively.

8.4 Pharmacokinetic Concentrations

Plasma and BAL concentrations of verproside and picroside II will be determined at the collection times and per the bioanalytic method described in [Section 8.1](#) and [Section 8.2](#), respectively. Plasma concentrations of verproside and picroside II will be used for the calculation of the plasma verproside and picroside II PK parameters. BAL concentrations of verproside and picroside II will be reported, but no PK parameters will be calculated.

8.5 Noncompartmental Pharmacokinetic Analysis and Parameter Calculation

8.5.1 Plasma Pharmacokinetic Parameters

The appropriate noncompartmental PK parameters will be calculated from the plasma verproside and picroside II concentration-time data following administration of YLP-001 on Days 1 and 54 (± 1) or Day 56, as well as predose concentrations in morning of Days 15 (± 2), 29 (± 2), 43 (± 2), and 54 (± 1) or Day 56 using Phoenix® WinNonlin® Version 6.3 or higher. All PK parameters included in the protocol are listed in Table 2 below, and are defined as appropriate for study design. Other PK parameters may be calculated if deemed appropriate and requested by the sponsor and agreed upon by Celerion.

Table 2 Noncompartmental Pharmacokinetic Parameters to be Calculated

Following a Single Dose of YLP-001 - Day 1			
Parameter	Label to be Used in Post-Text Tables	Definition	Method of Determination
AUC ₀₋₁₂	AUC0-12	Area under the drug concentration-time curve (AUC) from time zero to 12 hours.	Calculated using the Linear Trapezoidal with Linear Interpolation Method. May be extrapolated using the terminal elimination rate constant (k_{el}), if last measurable concentration (C_t) occurs prior to 12 hours postdose.
AUC _{0-t}	AUC0-t	AUC from time zero to time t , where t is the time of the C_t . This parameter will be reported only if plasma concentrations fall below the lower limit of quantitation before the last time point prior to the evening drug administration on Day 1 for at least one patient. Otherwise, only AUC ₀₋₁₂ will be reported.	Calculated using the Linear Trapezoidal with Linear Interpolation Method.
AUC _{0-inf}	AUCinf	AUC from time 0 extrapolated to infinity.	Calculated as: $AUC_{0-t} + C_t/k_{el}$
C _{max}	Cmax	Maximum observed drug concentration.	Taken directly from bioanalytical data.

Following a Single Dose of YLP-001 - Day 1			
Parameter	Label to be Used in Post-Text Tables	Definition	Method of Determination
t_{\max}	t_{\max}	Time of the maximum drug concentration (obtained without interpolation).	Observed
k_{el}	k_{el}	Apparent first-order terminal elimination rate constant, which represents the fraction of drug eliminated per unit time.	Calculated from a semi-log plot of the plasma concentration versus time curve, calculated by linear least-squares regression analysis using the maximum number of points in the terminal log linear phase (e.g., three or more non-zero plasma concentrations).
$t_{1/2}$	$t_{1/2}$	Apparent first-order elimination half-life.	Calculated as: $\ln(2)/k_{el}$
CL/F	CL/F	Apparent total plasma clearance after extravascular administration (verproside only).	Calculated as: $Dose/AUC_{0-\infty}$
V_z/F	V_z/F	Apparent volume of distribution during the terminal elimination phase after extravascular administration (verproside only).	Calculated as: $Dose/(k_{el} \times AUC_{0-\infty})$

Following Multiple Doses of YLP-001 - Day 54 (\pm 1) or Day 56			
Parameter	Label to be Used in Tables	Definition	Method of Determination
AUC _τ	AUCtau	AUC over the final 12-hour dosing interval (τ) at steady state (e.g., 0-12 hours).	Calculated using the Linear Trapezoidal with Linear Interpolation Method. May be extrapolated using the k_{el} , if C_t occurs prior to 12 hours postdose.
AUC _{0-t}	AUC0-t	AUC from time zero to time t , where t is the time of the C_t .	Calculated using the Linear Trapezoidal with Linear Interpolation Method.
C _{max_ss}	Cmax_ss	Maximum observed plasma concentration during a dosing interval at steady state.	Taken directly from bioanalytical data.
C _{min_ss}	Cmin,ss	Minimum observed/measured non-zero concentration during a dosing interval at steady state.	Taken directly from bioanalytical data.
t _{max_ss}	tmax_ss	Time to reach C _{max_ss} (obtained without interpolation).	Observed
C _{trough}	Ctrough	Plasma concentration observed at the end of a dosing interval at steady state. Presented as predose in the morning Days 15 (\pm 2), 29 (\pm 2), 43 (\pm 2), and 54 (\pm 2) (following PM dosing on Days 14 (\pm 2), 28 (\pm 2), 42 (\pm 2), and 54 (\pm 1) or 56, respectively).	Taken directly from bioanalytical data.
C _{avg_ss}	Cavg_ss	Average plasma concentration at steady state.	Calculated as: AUC_{τ}/τ
%Fluc	%Fluc	Percent peak-to-trough fluctuation at steady-state.	Calculated as: $(C_{max_ss} - C_{min_ss})/C_{avg_ss} \times 100$
Swing	Swing	Percent swing at steady-state.	Calculated as: $(C_{max_ss} - C_{min_ss})/C_{min_ss} \times 100$

Following Multiple Doses of YLP-001 - Day 54 (\pm 1) or Day 56			
Parameter	Label to be Used in Tables	Definition	Method of Determination
k_{el}	kel	Apparent first-order terminal elimination rate constant, which represents the fraction of drug eliminated per unit time.	Calculated from a semi-log plot of the plasma concentration versus time curve, calculated by linear least-squares regression analysis using the maximum number of points in the terminal log linear phase (e.g., three or more non-zero plasma concentrations).
$t_{1/2}$	$t_{1/2}$	Apparent first-order elimination half-life.	Calculated as: $\ln(2)/k_{el}$
CL_{ss}/F	CL_{ss}/F	Total body clearance estimated at steady-state after oral administration (verproside only).	Calculated as: $Dose/AUC_{\tau}$
$R_{A,AUC}$	RA,AUC	Accumulation ratio	Calculated as: AUC_{τ} / AUC_{0-12} (on Day 1) If AUC_{0-12} on Day 1 or AUC_{τ} on Day 54 (\pm 1) or 56 cannot be calculated for a patient, then no $R_{A,AUC}$ value will be presented for that patient.
$V_{z,ss}/F$	$Vz,ss/F$	Apparent volume of distribution at steady state.	Calculated as: $(CL_{ss}/F)/k_{el}$

For the calculation of the PK parameters that depended on the dose (CL/F , V_z/F , CL_{ss}/F , and $V_{z,ss}/F$) verproside content is 28.96 and 57.92 mg for the 80 and 160 mg YPL-001 dose levels, respectively.

Actual sample times will be used in the calculations. Patients for whom there are insufficient data to calculate the PK parameters (at least 3 consecutive measurable concentrations) will be included in the concentration tables only and excluded from the pharmacokinetic and statistical analyses.

For the calculation of the PK parameters, plasma concentrations below the limit of quantitation (BLQ) prior to the first quantifiable concentration will be set to 0.00 and plasma concentrations BLQ after the first quantifiable concentration will be treated as missing.

Plasma verproside and picroside II C_{trough} concentrations will be presented. Although C_{trough} concentrations are related to the PM dose given on Days 14 (\pm 2), 28 (\pm 2), 42 (\pm 2), and 53 (\pm 2), they will be labeled and referred with in the TFLs as AM predose time point on Days 15 (\pm 2), 29 (\pm 2), 43 (\pm 2), and 54 (\pm 1) or Day 56.

For the calculation of summary statistics and PK parameters, BLQ plasma concentrations will generally be set to 0 prior to the first quantifiable concentration on each study day and to missing thereafter. Based on the reported mean $t_{1/2}$ of plasma verproside and picroside II following the BID administration of 80 mg YPL-001 in a previous multiple ascending dose (MAD) study in healthy subjects, C_{trough} that are BLQ may be expected in this study. Therefore, C_{trough} BLQ concentrations measured at predose on Days 15 (± 2), 29 (± 2), 43 (± 2), and 54 (± 1) or Day 56 will be set to 0 for the calculations of summary statistics and PK parameters.

The k_{el} will be determined using linear regressions composed of least 3 data points. The k_{el} will not be assigned if 1) the terminal elimination phase is not apparent, 2) if t_{max} is one of the 3 last data points, or 3) if the R^2 value is less than 0.8. For the analysis on Day 1, the k_{el} will only be reported if the $t_{1/2}$ of verproside or picroside II can be appropriately estimated from a 12-hour sampling period following dosing. In cases where the k_{el} interval is not assigned, the values of AUC_{0-inf} , $t_{1/2}$, CL/F , V_z/F , AUC_τ , CL_{ss}/F , V_{z_ss}/F , and $R_{A,AUC}$, as applicable, are considered not calculable and will not be reported. Wherever the resulting $t_{1/2}$ is more than half as long as the sampling interval, the k_{el} values and associated parameters (AUC_{0-inf} , $t_{1/2}$, CL/F , V_z/F , AUC_τ , CL_{ss}/F , V_{z_ss}/F , and $R_{A,AUC}$ as applicable) may not be presented as judged appropriate and in accordance with Celerion SOPs.

All available data will be included in the concentration and PK parameter tables to the extent possible. Patients will be excluded from the PK population if they significantly violate a protocol inclusion or exclusion criteria, deviate significantly from the protocol, or if data are unavailable or incomplete, which may influence the PK analysis.

Except if otherwise specified, available concentration and PK data of each patient will be included in the summary statistics and statistical comparisons for PK parameters.

Data from patients who experience emesis within 1.5 hours following YPL-001 dosing (i.e., a period of time equal to 2 times the estimated t_{max} of verproside and picroside II) during the PK sampling periods (i.e., after AM dosing on Days 1 or 54 [± 1] or Day 56, as appropriate) may be excluded from the summary statistics for the given day and from the statistical comparison of PK parameters.

Any patient or data excluded from the PK analysis, summary statistics or statistical analysis will be identified, along with their reason for exclusion, in the CSR.

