4. ANALYSIS POPULATIONS

4.1 Analysis Populations

Safety population: All available data for patients who received at least one dose of the investigational product (i.e., YPL-001) or placebo. Safety data for all discontinued patients will be included in this set for the time points for which their data are available.

Symptom monitoring population: All available data for patients who received at least one dose of the investigational product (i.e., YPL-001) or placebo. Symptom monitoring data for all discontinued patients will be included in this set for the time points for which their data are available.

PK population: All patients receiving at least one dose of YPL-001 and having at least one measurable plasma concentration of verproside and picroside II.

PK per-protocol population: All protocol-compliant patients who received all scheduled doses of YPL-001 and have sufficient samples collected to determine PK parameters from plasma concentrations of verproside and picroside II on at least one of the two PK days (Days 1 and 54 (± 1 day) or 56).

PD population: All patients who received at least one dose of YPL-001 or placebo and provide at least one post-baseline PD measurement.

PD per-protocol population: All protocol-compliant patients who received all scheduled doses of YPL-001 or placebo and have measurable PD data.

PK/PD population: All patients who received at least one dose of YPL-001 and having any measurable concentration of verproside and picroside II and measurable PD data will be included in the PK/PD relationship assessment, as applicable.

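### The three-level rule in SAP Section 8.5.1 excludes patients, not profiles or parameters, so it can discard a valid Cmax_ss and, if 80 mg peaks lie near the LLOQ, bias the 160/80 mg ratio downward

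*SAP*

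**What the plan says.** Section 8.5.1 reads: "Patients for whom there are insufficient data to calculate the PK parameters (at least 3 consecutive measurable concentrations"), after which such patients "will be included in the concentration tables only and excluded from the pharmacokinetic and statistical analyses". The unit is the patient.

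Other parts of the SAP bear on the same decision:

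- **Section 4.1, PK population:** patients dosed with YPL-001 and "having at least one measurable plasma concentration of verproside and picroside II".
- **Section 4.1, PK per-protocol population:** compliant, fully dosed patients with "sufficient samples collected to determine PK parameters from plasma concentrations of verproside and picroside II on at least one of the two PK days".
- **Section 8.5.1, Table 2:** Cmax_ss is the "Maximum observed plasma concentration during a dosing interval at steady state", taken straight from the bioanalytical data.
- **Section 8.5.1, after Table 2:** "All available data will be included in the concentration and PK parameter tables to the extent possible", and then "Except if otherwise specified, available concentration and PK data of each patient will be included" in the summary statistics and comparisons.
- **Section 8.6:** PK-population patients outside the per-protocol set stay in the PK parameter listings and leave only the summary statistics.
- **Section 8.7:** AUCτ, AUC0-t and Cmax_ss are compared between 160 mg and 80 mg after dose normalisation, as a geometric mean ratio (GMR) with a 90% CI.

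**The concern.** Three consecutive levels are a sensible minimum for kel and AUC, but Cmax_ss needs only one. Section 8.5.1 already withholds AUCτ, clearance and volume when kel cannot be assigned. What the patient-level rule adds is the loss of parameters that do not need kel, and Cmax_ss is one of the three that Section 8.7 compares.

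The trigger is low exposure, which is the quantity under study, and it is met more often at half the dose. Losing low values mainly from the 80 mg reference arm raises that arm's geometric mean. Exactly proportional exposure would then read as less than proportional.

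The *and* in Section 4.1 raises the same issue between analytes. Both share one LLOQ, and Section 8.3 notes that "YPL-001 contains additional iridoids in lesser relative amounts" than verproside. Taken literally, a patient with good verproside data but no measurable picroside II is outside the PK population.

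**Working it through.** **Consistency of the text.** Take a patient with one or two measurable levels of each analyte.

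- Section 4.1 puts this patient in the PK population.
- Section 8.6 then keeps the patient in the PK parameter listings.
- Section 8.5.1 allows the concentration tables only.

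The last two cannot both be followed. The general inclusion sentence in Section 8.5.1 does not settle it, because it yields to anything otherwise specified and the three-level rule is such a specification. Section 4.1 accepts sufficient data on either PK day, whereas the three-level rule does not say which day's failure counts.

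**Size.** The SAP states no Cmax, exclusion rate or expected ratio, so there is no figure to reproduce.

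Inputs from the SAP:

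- LLOQ 50 pg/mL for both analytes (Section 8.2)
- 16 postdose samples (Section 8.1.1)
- tmax = 1.5 h / 2 = 0.75 h (emesis rule, Section 8.5.1)
- verproside content ratio 57.92 / 28.96 = 2 (Section 8.3)
- 20 patients per arm (Section 3)

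Assumptions not in the SAP: a one-compartment profile, proportional PK, half-life 1-2 h, residual error 15-30%, and the between-patient spreads shown below.

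Model: true 80 mg Cmax = m × 50 × exp(s·Z), with twice that at 160 mg. A level counts as measurable at 50 pg/mL or above. GMR = exp(mean ln(Cmax_160 / 2) − mean ln(Cmax_80)) among retained patients, with a true value of 1.

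For a log SD of 0.6:

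| Median 80 mg Cmax | Dropped at 80 mg | GMR, 3-level rule | GMR, one level suffices |
|---|---|---|---|
| 2 × LLOQ | 18-22% | 0.83-0.85 | 0.90-0.93 |
| 3 × LLOQ | 6-8% | 0.92-0.94 | 0.97 |
| 5 × LLOQ | about 1% | 0.98-0.99 | – |
| 10 × LLOQ | none | 1.00 | 1.00 |

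Sensitivity to spread (half-life 1 h, residual error 20%):

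| Median 80 mg Cmax | CV | Dropped, 80 / 160 mg | GMR, 3-level rule | GMR, one level suffices |
|---|---|---|---|---|
| 2 × LLOQ | 50% | 14.4% / 0.7% | 0.89 | 0.95 |
| 2 × LLOQ | 100% | 26.9% / 7.6% | 0.78 | 0.84 |
| 5 × LLOQ | 50% | 0.2% / 0% | 1.00 | 1.00 |
| 5 × LLOQ | 100% | 4.4% / 0.6% | 0.93 | 0.97 |
| 10 × LLOQ | 100% | 0.5% / 0% | 0.99 | 0.99 |

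**In patients.** With 20 per arm, losing the lowest 1, 2 or 3 patients at 80 mg gives an expected GMR of 0.955, 0.918 or 0.885 (CV 50%). At CV 100% it is 0.922, 0.860 or 0.806. The 90% CI half-width factor is exp(1.686 × s × √(2/20)), with s = √ln(1 + CV²). For s = 0.472 this is 1.29, and for s = 0.833 it is 1.56.

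**Two-analyte wording, read literally.** Let p be the share of the 80 mg arm without measurable picroside II, z the matching normal quantile, log SD 0.6 and between-analyte correlation 0.7. The log shift at 80 mg is 0.7 × 0.6 × φ(z)/(1 − p). The same term at z − ln(2)/0.6 applies to 160 mg.

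- p = 5%: z = −1.645, and 0.42 × (0.1086 − 0.0079) = 0.042, so the verproside GMR = exp(−0.042) = 0.96.
- p = 10%: 0.93.
- p = 20%: 0.88.

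**The case against.** The strongest reply is that the rule may never bite. Section 8.5.1 refers to a mean half-life for both analytes from an earlier study at 80 mg BID, and estimating one takes several measurable points after the peak. The only BLQ values it expects are troughs. With a 2 h half-life, a trough 12 h postdose is BLQ for any Cmax up to about 44 times the LLOQ under the same model, far above the range where the three-level rule matters. This stands as an argument about likelihood. It does not settle the matter, because no Cmax is given.

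A reader might infer that PK inclusion in this SAP is set per patient throughout. The document does not support that. The kel rule drops listed parameters. The accumulation ratio alone is omitted when one day's AUC is missing, which presupposes that the patient stays in, so it is a strained reading that a poor Day 1 profile must remove a good Day 54/56 profile. Emesis exclusion from summary statistics is by day. PK tables are separate by analyte, and the Table 11-11 shell prints N for each parameter. The defect lies in the three-level sentence and the Section 4.1 wording.

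The *and* may be no more than the SAP's stock phrase for its two analytes. The PK population also needs only one measurable level among 2 × 17 + 3 = 37 scheduled samples. About 6%, 1.5% and 0.1% of 80 mg patients would have none at median peaks of 2, 3 and 5 times the LLOQ, so losses of 5-20% need picroside II peaks at about 2 times or below. Section 8.3 describes drug content, not plasma level.

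PK is exploratory, the ratio has no acceptance bounds, and a CI factor of 1.29-1.56 exceeds most of the shifts above. Section 8.5.1 also requires exclusions to be reported with reasons. Reporting discloses a loss but does not undo it, and the contradiction with Section 8.6 exists whatever Cmax proves to be.

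**Conclusion.** The point stands as a badly specified rule with a conditional bias. The rule can discard a valid Cmax_ss, contradicts Section 8.6 and sits badly with the either-day wording of Section 4.1. Where it bites, it falls mainly on low-exposure 80 mg patients and lowers the dose-normalised 160/80 mg Cmax_ss ratio. At log SD 0.6 the ratio reads about 0.85, 0.93 and 0.98-0.99 at median 80 mg peaks of 2, 3 and 5 times the LLOQ. Above about 5-10 times the effect is negligible, and wider between-patient spread moves that threshold towards the upper end.

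It would go too far to say that the rule does remove low-exposure patients and does lower the ratio. The SAP gives no Cmax, and the sizes rest on assumed half-life, spread, residual error and correlation. The severity is minor to moderate.

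**What to change.** - **Section 8.5.1:** apply the three-consecutive-level rule by analyte, PK day and parameter, so that it bars only kel, AUC and derived parameters for that profile. Report Cmax, Cmax_ss and tmax for every profile with at least one measurable level, and let Cmax_ss enter the Section 8.7 ANOVA.
- **Section 4.1:** define the PK and PK per-protocol populations separately for verproside and picroside II.
- **Sections 4.1, 8.5.1 and 8.6:** reconcile the either-day wording, the three-level rule, the all-available-data sentences and the listing rule.
- **Tables 11-13 and 11-17:** show N per parameter and arm. The Table 11-13 shell, which Table 11-17 follows, has one N per treatment.

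The cost is some SAP wording and a flag in the PK dataset, to be settled before concentrations are seen. N may then differ between parameters in one table.

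The gain is partial. At 2 times the LLOQ and CV 50%, 10.0 of the 14.4 percentage points dropped at 80 mg had a measurable level and would return, and the Cmax_ss GMR moves from 0.89 to 0.95. Patients with no measurable level still have no ln(Cmax_ss), and AUCτ and AUC0-t gain nothing from the change to the three-level rule.

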8.7 Statistical Analysis of Pharmacokinetic Parameters

An estimate of the relative systemic exposure after multiple dose administration of YLP-001 using plasma verproside and picroside II AUC_{τ} , AUC_{0-t} , and C_{max_ss} on Day 54 (± 1) or Day 56 will be performed by dose-normalized (to 80 mg YLP-001) ratio analysis (i.e., parameter values for 160 mg versus parameter values for 80 mg; Treatment B Versus Treatment A), expressing the geometric mean ratio (GMR) and 90% confidence interval (CI) of the GMR.

The ANOVA analysis will be performed using the following SAS[®] code:

```
PROC MIXED;  
CLASS TREATMENT SUBJECT;  
MODEL PK_PARAMETER = TREATMENT;  
ESTIMATE "B vs A" TREATMENT -1 1 / cl alpha=0.1 e;  
LSMEANS TREATMENT / cl;
```

Note: Parameters will be dose-normalized to 80 mg YLP-001, prior to analysis.

Additional analyses may be performed as deemed necessary upon review of the data and/or upon Sponsor's request.

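### SAP Section 8.5.1 withholds AUCtau, CLss/F and R_A,AUC when kel is not assigned, although its own Table 2 needs no kel for AUCtau when the 12 h concentration is measurable

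*SAP*

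**What the plan says.** SAP Section 8.5.1, Table 2, defines the Day 54/56 parameter as "AUC over the final 12-hour dosing interval", obtained by linear trapezoid, and adds: "May be extrapolated using the k_{el} , if C_t occurs prior to 12 hours postdose". The Day 1 counterpart, AUC0-12, is the "Area under the drug concentration-time curve (AUC) from time zero to 12 hours", with the same method and the same optional extrapolation. Table 2 derives CLss/F (verproside only) as dose over AUCtau, and R_A,AUC as AUCtau over Day 1 AUC0-12. It blanks R_A,AUC only where one of those two areas cannot be calculated.

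The text after the table sets two rules.

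- **kel not assigned.** This happens when no terminal phase is visible, or "if t_{max} is one of the 3 last data points, or 3) if the R^2 value is less than 0.8". AUCtau, CLss/F and R_A,AUC then stand in a list of values that, "as applicable, are considered not calculable and will not be reported".
- **Long half-life.** Where the estimated half-life "is more than half as long as the sampling interval", kel and the same list of parameters "may not be presented as judged appropriate and in accordance with Celerion SOPs".

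AUC0-12, AUC0-t, Cmax_ss, C_avg_ss and %Fluc are in neither list. Section 8.7 describes the dose comparison as "An estimate of the relative systemic exposure after multiple dose administration of YLP-001" and uses AUCtau, AUC0-t and Cmax_ss.

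**The concern.** A trapezoidal area to 12 h is fully determined by the observed concentrations when the 12 h sample is quantifiable. Calling it not calculable for want of a terminal slope is wrong under the SAP's own method. A programmer following the text would print AUC0-t for a patient and blank AUCtau beside it, although at nominal times the two are the same number.

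The omission also depends on the patient's kinetics. A tmax among the last three samples marks a late absorber. A half-life above 6 h marks a patient who accumulates, and R_A,AUC is the plan's only AUC-based accumulation measure. Because the second rule is a matter of judgement, it can be applied after the values have been seen. C_avg_ss and %Fluc are calculated from AUCtau, and the SAP does not say what happens to them when AUCtau is withheld.

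**Working it through.** The SAP states no figure on this point, so there is none to reproduce. The check sets its rules side by side and then sizes the half-life rule.

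**Inputs from the SAP.** Last three nominal sampling times 8, 10 and 12 h (Section 8.1.1); LLOQ 50.0 pg/mL (8.2); verproside content 28.96 mg at the 80 mg dose (8.3); dosing interval 12 h; 20 patients per arm (Section 3). Emesis window of 1.5 h, set at twice the estimated tmax, so tmax = 1.5/2 = 0.75 h (8.5.1). No half-life is given; all half-lives below are assumptions.

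**1. Is kel needed?** By Table 2, only if the last measurable concentration precedes 12 h. The suppression sentence carries no such limit. Linear trapezoids on the 17 nominal times, using no kel, were compared with the exact steady-state area Dose/CL for assumed one-compartment profiles (volume 20,000 L):

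| Assumed profile | tmax (h) | C12 (pg/mL) | Trapezoid / exact (pg·h/mL) | Ratio |
|---|---|---|---|---|
| Half-life 8 h | 1.5 | 828 | 16,713 / 16,712 | 1.000 |
| Late absorption, half-life 2 h | 8 | 337 | 4,411 / 4,178 | 1.056 |
| Late absorption, half-life 3 h | 10 | 763 | 5,791 / 6,267 | 0.924 |

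Both late-absorption profiles fail the tmax criterion. In the third, a line through the last three log-concentrations also slopes upward, with R² 0.64. AUCtau is still obtainable in each. By contrast, an ordinary profile with half-life 2 h and tmax 0.75 h has C12 = 26 pg/mL, below the LLOQ. There kel is needed, and suppression agrees with Table 2.

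**2. Half-life cut-off.** 12/2 = 6 h.

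**3. Accumulation at the cut-off.** R_A = 1/(1 − 2^(−12/t½)). At t½ = 2, 3, 4, 6, 8 and 12 h this gives 1.02, 1.07, 1.14, 1.33, 1.55 and 2.00. A half-life above 6 h therefore corresponds to R_A above 1.33.

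**4. Size if the half-life rule were always applied.** Log-normal half-lives, CV 30% to 50%, AUCtau taken as proportional to half-life (400,000 draws per case):

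| Median t½ | Share above 6 h | Geometric mean AUCtau lower by |
|---|---|---|
| 2 h | 0.01-1.0% | 0.0-1.3% |
| 3 h | 0.9-7.1% | 0.7-6.6% |
| 4 h | 8.4-19.5% | 4.8-14.9% |
| 5 h | 26.8-35.1% | 12.4-23.7% |

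**5. What remains in the dose comparison.** With a measurable 12 h sample, t = 12 h in AUC0-t, so AUC0-t equals AUCtau at nominal times. AUC0-t and Cmax_ss are not suppressed, and R_A,AUC is not part of that comparison.

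**The case against.** The best defence is that the qualifier at the start of "as applicable, are considered not calculable and will not be reported" already confines the rule to profiles that need extrapolation. The SAP expects troughs below quantitation, and in those patients AUCtau to 12 h does require kel. The second half of that stands. The first does not: the qualifier can just as well sort Day 1 from steady-state parameters, AUCtau is named outright, and nothing mentions profiles ending before 12 h.

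Three stronger readings are tempting, and the documents do not support them.

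- A reader might infer that AUCtau is discarded whenever half-life exceeds 6 h. The wording is permissive ("may not be presented as judged appropriate and in accordance with Celerion SOPs"). The fault there is an unfixed choice, not automatic loss.
- A reader might infer that late-absorbing or accumulating patients leave the dose comparison. They leave its AUCtau line only, and AUC0-t carries the same area for them.
- A reader might take the 4-5 h rows as the expected understatement of exposure, or infer a B/A ratio pulled towards dose proportionality. Those rows assume that the rule is always applied and that all variation in half-life comes from clearance; if it came from volume, AUCtau would not change. The 0.75 h tmax and expected unquantifiable troughs point to the shorter half-lives, although the trough expectation comes from healthy subjects at 80 mg. Late absorption at unchanged clearance and bioavailability leaves steady-state AUCtau unchanged, so no direction of bias is shown for the rule on unassigned kel. Equal loss in both arms largely cancels in the ratio.

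It is also fair to say that PK is exploratory here, and that Section 8.5.1 requires excluded data and reasons to be identified in the CSR.

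**Conclusion.** Section 8.5.1 contradicts its own Table 2. As written, it withholds AUCtau, CLss/F and R_A,AUC from patients in whom they can be calculated, while keeping the identically computed Day 1 AUC0-12. This part needs no assumption. The half-life sentence adds a discretionary route by which the accumulation ratio could be withheld, after the fact, from the patients who accumulate most.

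The loss is limited to those three parameters, possibly C_avg_ss and %Fluc, and the AUCtau line of the B versus A analysis. Its size cannot be fixed from the SAP. If the discretionary rule were always applied, it would remove about 0-7% of patients at median half-lives of 2-3 h and about 8-35% at 4-5 h, under the assumptions shown. No frequency can be put on the rule for unassigned kel. The B/A ratio is biased only if the loss differs by dose, and nothing in the SAP shows that it would. The primary safety and secondary symptom endpoints are untouched. The text should still be corrected, because it discards valid data in arms of at most 20 patients.

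**What to change.** In Section 8.5.1:

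1. In both suppression sentences, restrict the condition on AUCtau, CLss/F and R_A,AUC to profiles whose last measurable concentration falls before 12 h, so that kel was needed to extrapolate.
2. Apply the same rule to Day 1 AUC0-12.
3. State that C_avg_ss and %Fluc are reported whenever AUCtau is.
4. Make whatever remains of the half-life rule fixed, with its consequence written in the SAP rather than left to judgement.
5. Keep suppression without a valid kel for AUC0-inf, t1/2, CL/F, Vz/F and Vz_ss/F.

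The cost is a rewording of two sentences, a line on the derived parameters and one programming flag. No new data are needed.
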